4.3 Analysis Populations

The intent-to-treat (ITT) population, per protocol (PP) population, and Completer2 and Completer5 populations are defined as follows:

ITT Population: All subjects who receive at least one Sculptra® Aesthetic injection

PP Population: All subjects who receive at least one Sculptra® Aesthetic injection and are without any major protocol deviation. Protocol deviations will be reviewed by the Sponsor/CRO to determine which subjects will be included in the PP population.

PP population based analysis will only be done if the number of subjects from PP population is at least 5% different from the ITT population.

Completer2 Population: All subjects who receive at least one Sculptra® Aesthetic injection and finish the second year visit. Subjects who finish the second year visit are those who did not discontinue before Day 703 (Day 731 - 4 weeks).

Completer5 Population: All subjects who receive at least one Sculptra® Aesthetic injection and completed the study.

4.3.1 Efficacy populations

The analysis population for efficacy will be the ITT population and the PP population. The ITT population is the primary population for hypothesis testing.

4.3.2 Safety populations

The analysis population for safety will include the ITT population and the PP population. The ITT population is the primary population for hypothesis testing. The Completer2 and Completer5 populations will be used for sensitivity analyses of the primary and secondary hypotheses.

4.3.4 Disposition of subjects

The general disposition of subjects during the study will be defined as follows: (a) **screened** subjects are those who have a written informed consent document; (b) **treated** subjects are those screened subjects who received at least 1 dose of Sculptra® Aesthetic; and (c) **completed** subjects are those treated subjects who complete all clinical trial protocol required visits.

4.4.1 Demographics and baseline characteristics

Demographics and baseline characteristics will be summarized by descriptive statistics, which consist of mean, standard deviation, median, minimum and maximum for continuous variables, and frequency count and percentage for categorical variables.

A listing of concomitant medication that were used for injection site nodule and/or papule will be provided. These medications will be determined from a manual review of the indications reported for all medications that were used for treatment of an AE.

4.4.2 Extent of study treatment exposure and compliance

Extent of treatment exposure and compliance will be determined by the number of injection sessions, the total amount of Sculptra® Aesthetic (mL) used, the total amount of Sculptra® Aesthetic used per anatomic area and per injection session, and the amount of Sculptra® Aesthetic used per surface area (mL/cm²) per WAS.

Volume per surface area will be calculated by taking the amount volume injected at a given injection area and in a given injection session. In the case where a given area has multiple injections, volume per surface area for this area will be calculated by obtaining volume per surface area for each session independently, and then averaging across all injections the area receives.

[figure not shown]
The treatment exposure and compliance will also be summarized by whether the area treated developed any injection site nodules and/or papules. Specifically, number of injections, total treatment volume (mL), volume per surface area (mL/cm²), and volume per surface area by study center will be summarized in subgroups that are defined by whether the injection site had an injection site nodule and/or papule. These summaries will be done overall and by anatomic area.

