Subjects treated with Sculptra® Aesthetic and Cosmoplast during the controlled phase showed a consistent, progressive, and significant improvement over baseline for the primary variable WAS beginning 3 weeks after the last treatment. Though the treatment effect of Sculptra® Aesthetic was maintained for up to 13 months, the Cosmoplast treatment effect returned to baseline within 3 months of the final treatment.

Commonly occurring short-term injection-related site reactions were reported in both treatment groups. In this clinical study the percentage of subjects with nodules and/or papules was greater after Sculptra® Aesthetic (17.2% [20 of 116]) than after the control treatment (12.8% [15 of 117]). This reflects 8 Sculptra® Aesthetic subjects who experienced nodules, 10 Sculptra® Aesthetic subjects who experienced papules, and 2 Sculptra® Aesthetic subjects who experienced both nodules and papules. After the first Sculptra® Aesthetic injection session, time to onset for nodules was 160 days (median) and 209 days (mean), and for papules, time to onset was 55 days (median) and 159 days (mean). After Sculptra® Aesthetic injection, the duration of nodules was 100 days (median) and 180 (mean) days, and for papules, was 110 days (median) and 176 days (mean). One subject with a papule required a single intralesional corticosteroid injection and the event resolved. For 3 subjects with nodules/papules, no information on outcome was available at the end of the 25-month extension phase study. For all remaining subjects, nodules/papules resolved spontaneously. None of these events were reported as a serious adverse event by the investigator. Table 3 shows adverse event data that were collected from patient diaries over the controlled phase (0 to 13 months Sculptra® Aesthetic versus Cosmoplast).

CONFIDENTIAL

Table 3 - Intensity of adverse events after the initial treatment session, recorded in the 14 day subject diary (Controlled Phase) - All-Treated Population

SCULPTRA Aesthetic (First Treatment Session: N = 116)						Cosmoplast (First Treatment Session: N = 117)						
		Severity of A	dverse Eve	nt ^a			Severity of Adverse Event ^a					
Injection Procedure Related Event	Total subjects reporting symptoms ^a n (%)	Mild n	Moderate n	Severe n	Missing n	Total subjects reporting symptoms ^a n (%)	Mild n	Moderate n	Severe n	Missing n		
Localized Swelling	94 (81.0)	64	24	5	1	76 (65.0)	60	13	1	2		
Localized Tenderness	94 (81.0)	63	24	2	5	83 (70.9)	62	16	1	4		

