8 TREATMENTS

8.1 INVESTIGATIONAL PRODUCT

The Sponsor will supply the Sculptra® Aesthetic and the sterile water for injection (SWFI). Only Sculptra® Aesthetic and SWFI provided by the Sponsor can be used for this study.

The investigational site will supply the syringes and other materials needed for the injections, such as alcohol wipes and other types of topical/local anesthetics (if used). See

package insert for a complete list of required supplies. The investigational site will also be

Background therapy (eg, treatments for underlying disease) or other drug therapy not identified in this study protocol will not be supplied by the Sponsor.

responsible for proper disposal of syringes and any other biohazard material(s).

Sculptra® Aesthetic is an injectable implant that contains PLLA, a biocompatible, biodegradable, synthetic polymer from the alpha-hydroxy-acid family.

Protocol GLI.04.SPR.US10321

CONFIDENTIAL

Sculptra® Aesthetic is reconstituted with 5 mL sterile water for injection (SWFI) as outlined in the package insert.

Each subject will receive a single regimen of Sculptra® Aesthetic to correct shallow to deep (WAS 2 to 4) NLF contour deficiencies and, if present, other facial wrinkles for which grid pattern (cross-hatch) injection technique is appropriate (ie, marionette lines, cheek folds, and chin crease/chin fold with WAS between 2 and 4 on the applicable scale [see Appendix III]). A single regimen consists of up to 4 injection sessions with 3-week intervals, of multiple 0.1 to 0.2 mL deep dermal injections in a grid pattern, spaced at a distance of approximately 1 cm. A maximum of 10 mL (5 mL per side of the face), 2 vials of Sculptra® Aesthetic, is allowed at each injection session and is up to the discretion of the Investigator. A maximum of 2.5 mL may be placed in each NLF at each injection session. (For injection technique and procedures, see the Sculptra® Aesthetic Package insert). Only NLFs and other facial wrinkles treated during Visit 1 may be treated at subsequent visits.

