11.1 TEMPORARY TREATMENT DISCONTINUATION WITH INVESTIGATIONAL PRODUCT

Sculptra® Aesthetic use at specific sites in which an active inflammatory process (skin eruptions such as cysts, pimples, rashes or hives) or infection is present should be deferred until the inflammatory process has resolved and is controlled. This deferral will include the entire facial treatment (versus only the specific site with an active inflammatory process or infection).

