5.3 Relative Day Ranges and Visit Windows

If a subject discontinues early, the efficacy data (wrinkle assessments and investigator/subject global evaluations) from Visit 12 (Year 5) will be reassigned to a scheduled visit based on the relative ranges in the following table. If a result already exists for the calculated visit or the calculated visit was not a scheduled visit, the next scheduled visit will be assigned.

Relative day calculations will be the parameter visit date of interest minus the Study First Treatment Date plus one.

Table 1: Visit Collection Time and Relative Day Ranges

Collection Time (Target Day ± Visit Window)	Relative Day Ranges
Baseline (Day 1)	≤ Day 1
Week 3 (Day 22 ± 3 days)	Day 2 to Day 32
Week 6 (Day 43 ± 3 days)	Day 33 to Day 53
Week 9 (Day 64 ± 3 days)	Day 54 to Day 124
Month 6 (Day 184 ± 2 weeks)	Day 125 to Day 290
Month 13 (Day 397 ± 2 weeks)	Day 291 to Day 564
Year 2 (Day 731 ± 4 weeks)	Day 565 to Day 913
Year 3 (Day 1096 ± 4 weeks)	Day 914 to Day 1278
Year 4 (Day 1461 ± 4 weeks)	Day 1279 to Day 1643
Year 5 (Day 1826 ± 4 weeks)	≥ Day 1644

5.4 Calculation of Duration and Time to Onset:

Below are the rules on how duration and time to onset are calculated:

- 1. Duration = Event End Date Event Start Date + 1
 - For events that are ongoing, the formula will be updated per following scenarios:
 - a. If the subject had XXX visit, duration will be XXX visit date minus start date plus 1;
 - b. If the subject discontinued the study, duration will be discontinuation date minus event start date plus 1;

- c. If none of the above, the event's duration will be time of visit minus study day of event start date plus 1, where time of visit is defined as scheduled study day + 4 weeks (2 weeks for Month 13).
- 2. Time to Onset (from treatment) = Event Start Date Date of First Treatment.

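### The SAP 4.4.2 comparison of session counts and total volume by nodule/papule status counts sessions after lesion onset, so a modest dose relation could be hidden or reversed

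*SAP*

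**What the plan says.** SAP 4.4.2 takes number of injections, total volume and volume per surface area, and states that these "will be summarized in subgroups that are defined by whether the injection site had an injection site nodule and/or papule", overall and by anatomic area. The split is ever versus never. No lag, landmark or cut at lesion onset is given there or elsewhere in the readable text. Volume per surface area is computed for each session, "and then averaging across all injections the area receives".

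Protocol 8.1 sets the course: "A single regimen consists of up to 4 injection sessions with 3-week intervals". SAP 5.3 places the Week 9 visit at Day 64 ± 3 days. Protocol section 4 gives onset after the first session in the earlier US trial: nodules had a median of 160 and a mean of 209 days, and "for papules, time to onset was 55 days (median) and 159 days (mean").

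A lesion could cost a session in two ways. Protocol 11.1 defers treatment while an active inflammatory process or infection is present, and adds: "This deferral will include the entire facial treatment". Protocol 11.2.1 stops treatment at the subject's request or when the investigator judges continuation detrimental. Against this, the opening of Protocol section 11 asks that treatment continue where possible, and Protocol 8.1 ends sessions on wrinkle grade.

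**The concern.** A table of exposure by lesion status will be read as evidence on whether more product brings more nodules and papules. That reading requires the exposure to come before the lesion. Here the treatment period overlaps the period in which papules appear. Sessions given after onset are counted as if they could have caused the lesion. Sessions withheld because of the lesion make affected areas look less exposed. The second effect can make a true modest dose relation look absent, or make more product look protective. In a post-approval safety study that would be an unfortunate misreading, even of a descriptive table.

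**Working it through.** **Source figures.** In the earlier trial 8 + 10 + 2 = 20 subjects had a nodule, a papule or both, and 20/116 = 17.2%, as Protocol section 4 states. Of these, 12 of 20 had a papule, which gives a 60:40 papule:nodule mix below.

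**Onset before the last session.** Sessions fall 0, 21, 42 and 63 days after the first (Days 1, 22, 43, 64). A lognormal curve matches both stated figures, with log-SD = √(2 ln(mean/median)):

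- Papules: √(2 ln(159/55)) = 1.457
- Nodules: √(2 ln(209/160)) = 0.731

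The share starting before day t is Φ(ln(t/median)/log-SD):

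| Days after first session | Papules | Nodules |
|---|---|---|
| 21 | 25.4% | 0.3% |
| 42 | 42.7% | 3.4% |
| 63 | 53.7% | 10.1% |

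For the mix, 0.6 × 53.7% + 0.4 × 10.1% = 36%. If incidence were again 17.2% of the planned 863 subjects (148), about 54 would have a lesion starting before the Week 9 session.

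**Size of a false deficit with no dose effect.** Two assumptions are not in the documents: 2, 3 or 4 planned sessions in 20%, 30% and 50% of areas (mean 3.3), and every lesion stopping later sessions. "Number of injections" is taken as number of sessions. Expected sessions for K planned = 1 + the sum of P(no lesion yet) at each later session.

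- Papules: 1.746, 2.319 and 2.782 for K = 2, 3, 4. Weighted, 0.2 × 1.746 + 0.3 × 2.319 + 0.5 × 2.782 = 2.44. Deficit 0.86/3.3 = 26%.
- Nodules: 1.997, 2.964 and 3.862. Weighted, 3.22. Deficit 0.08/3.3 = 2%.
- 60:40 mix: (0.6 × 0.86 + 0.4 × 0.08)/3.3 = 17%.

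The deficit is proportional to the share of lesions that stop sessions. For the mix it is about 8% at one half, 4% at one quarter and 0 at none.

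**Effect on a true relation.** Simulation used the same onset mix, 17.2% incidence, a hazard ratio RR per extra session already received, and c for the share of lesions that stop later sessions. The table gives the difference in mean sessions, lesion minus lesion-free areas, over three patterns of planned sessions (means 2.5, 3.0 and 3.4):

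| RR | True difference (c = 0) | c = 0.5 | c = 1 |
|---|---|---|---|
| 1 | 0 | −0.32 to −0.18 | −0.64 to −0.37 |
| 1.25 | +0.12 to +0.24 | −0.10 to +0.09 | −0.34 to −0.07 |
| 1.5 | +0.22 to +0.44 | +0.04 to +0.31 | −0.14 to +0.17 |
| 2 | +0.35 to +0.75 | not needed here | +0.12 to +0.56 |

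**Does the remedy hold?** In a further run at RR 1.25, the all-session difference was +0.10, −0.12 and −0.34 at c = 0, 0.5 and 1. Comparing each lesion with areas still at risk on that day gave a steady +0.09. A landmark after the last session is also insensitive to c: +0.22 to +0.23 with a mean of 3.0 planned sessions. The two differ in size because the landmark omits early lesions and the session patterns differ, but neither depends on the unknown c.

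**The case against.** The strongest objection is that the step from lesion to lost session is assumed. Protocol 11.1 gives cysts, pimples, rashes and hives as examples and does not name nodules or papules. It speaks of deferral until resolution, not cancellation. Protocol section 11 makes permanent discontinuation a last resort. This stands: c is unknown, and at c = 0 the session count is not biased. A reader might infer that the protocol withdraws sessions once a nodule or papule appears; the text does not say so.

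Three further inferences also go too far.

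- *All three measures are biased.* Volume per surface area is averaged over sessions, so a lost session does not mechanically lower it. What remains is that one session and four equal sessions give the same value.
- *Nodules are affected much as papules are.* Exponential curves fitted to the medians alone would put 24% of nodules before Day 64 and give roughly a 10% deficit. But they imply means of 55/ln 2 = 79 days for papules and 160/ln 2 = 231 for nodules, against the stated 159 and 209.
- *Half of papules precede the area's last session.* That holds for four-session areas. With the assumed mix it is 0.2 × 25.4% + 0.3 × 42.7% + 0.5 × 53.7% = 45%.

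Two other points temper the size. Whole-face deferral also removes sessions from the subject's unaffected areas, which dilutes the contrast and was not modelled. The onset figures rest on 20 affected subjects. In addition, SAP 4.4.4.2 lists events leading to discontinuation of the product, so some of the mechanism would be visible. The section on the primary hypotheses is redacted, so a different dose analysis there cannot be excluded.

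**Conclusion.** The point holds for number of injections and total volume. Both are compared by ever/never lesion status with no regard to onset, while over half of papules and about a tenth of nodules would be expected before Day 64. If roughly a quarter to a half or more of early lesions end treatment, a modest relation (RR about 1.15 to 1.25 per session) can be hidden or reversed. At RR 2 it is weakened but not reversed. With no dose effect and every lesion stopping sessions, the false deficit is about 26% for papule areas and 2% for nodule areas.

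These sizes rest on the lognormal fit, the assumed session mix and the unstated c. The documents do not show that the bias will occur, only that the stated rule allows it. Nor does it touch the co-primary incidence endpoints: the table is descriptive and carries no test. It is an optional but worthwhile refinement.

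**What to change.** Add to SAP 4.4.2:

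1. First-session volume and mL/cm² by later lesion status. These precede every lesion and need no assumption about stopping.
2. Cumulative sessions, volume and summed mL/cm² up to the day before first onset. Compare each affected area with areas still lesion-free and under follow-up on that same study day, counted to that day. The comparator must be defined this way: cutting exposure at onset for affected areas alone would leave early cases with fewer sessions by construction. A simpler alternative is a landmark after the last possible session (Day 67 at the edge of the visit window), restricted to lesions starting later.

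Keep the whole-course totals, labelled as description only. Summed mL/cm² also supplies the cumulative density that the average does not show.

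Session dates (Protocol 8.6) and onset dates (Protocol 9.1.1) are already collected. The cost is SAP wording, a few derived variables and slightly more complex tables. The landmark version also sets aside the early lesions.

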4.4.4 Analysis of safety data

4.4.4.2 Other analyses of adverse events

All adverse events will be collected and summarized with the number of subjects reporting adverse events by number of injections, system organ class, preferred term, severity, relationship to the Sculptra® Aesthetic, and relationship to injection procedure.

For injection site nodules and/or papules and any other AEI, summaries will also include incidence rates by location and intervention, duration (<=30 days versus >30 days), and time to onset (<=30 versus >30 days for nodules and/or papules, and <=120 versus >120 days for any other AEI). Duration and time to onset of all events will also be summarized with descriptive statistics. Kaplan Meier estimates and plots will also be provided to estimate the maximum duration and time to the first occurrence within a subject. Time to onset is defined as the time from first injection to the start of the event.

To obtain duration of injection site nodules and/or papules and any other AEI, events that are ongoing will be handled in two ways: 1) excluding events that are ongoing at the time of data cutoff; and 2) assigning data cutoff date as the event end date.

The following frequency distributions of adverse events (incidence tables) will be provided:

- Overview of adverse events
- All AEs by number of injection sessions
- All AEs by system organ class and preferred term by decreasing frequency
- All AEs by system organ class, preferred term and intensity
- All AEs by system organ class, preferred term and relationship to treatment
- All AEs by system organ class, preferred term and relationship to procedure

The following listings will be provided:

- All adverse events
- Serious adverse events
- Adverse events that lead to discontinuation of Sculptra® Aesthetic
- Adverse events that lead to discontinuation of study
- Injection site nodules and papules
- AEI, other than injection site nodule and papule

The incidence rate of injection site nodule and/or papule will also be summarized by study site and baseline wrinkle assessment.

Subject reported injection related events collected in the diary card will be summarized by frequencies and percentages. Severity of subject reported injection related events after initial treatment session will be summarized by anatomic areas and Fitzpatrick skin type groups.

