Study treatment injections should be stopped when both NLFs and other facial wrinkles have reached a grade of 0 to 1 on the appropriate wrinkle assessment scale (see Appendix III and Appendix III). Correction should be limited to no more than 100% of the defect. (If only 1 wrinkle has reached the target grade of 0 to 1 the other side should continue to be treated until the target grade is achieved [or a maximum of 4 injection sessions and a maximum of 2.5 mL per NLF per session]).

The selection of topical and/or injectable anesthetic agents for local anesthesia will be at the discretion of the Investigator; however, injectable anesthetics should not be mixed into the Sculptra® Aesthetic vials.

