- Perform additional injections with Sculptra® Aesthetic in accordance with instructions for use. NOTE: Photographs must be taken of each area that is treated **prior** to any injection and **after** administration of Sculptra® Aesthetic (see the manual of photographic procedures), but not between administration of a local anesthetic and Sculptra® Aesthetic. If a local anesthetic is injected, then the WAS must be assessed, after administration of local anesthetic (prior to injection of Sculptra® Aesthetic), and after injection of Sculptra® Aesthetic.
- Distribute diary card.
- Subjects will be scheduled for next visit in three (3) weeks (± 3 days).

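### Does timing nodule and papule onset from the first injection hide lesions that arise soon after a repeat session?

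*SAP*

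**What the plan says.** SAP 4.4.4.2 plans, for injection site nodules and papules, incidence by "time to onset (<=30 versus >30 days for nodules and/or papules", with a separate 120-day split for the other adverse events of interest. The same section fixes the origin: "Time to onset is defined as the time from first injection to the start of the event". SAP 5.4 repeats it as a formula, "Time to Onset (from treatment) = Event Start Date" minus the date of first treatment. Alongside the split, SAP 4.4.4.2 provides descriptive statistics of onset time for all events, Kaplan-Meier estimates and plots of time to first occurrence within a subject, a listing of nodules and papules, and adverse events by number of injection sessions. SAP 4.4.2 adds number of injections, volume and volume per surface area according to whether the treated area developed a nodule or papule, overall and by anatomic area.

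Protocol 8.1 describes one regimen of up to four sessions at three-week intervals, and lets only wrinkles treated at Visit 1 be treated again. Table 1 of SAP 5.3 gives the later sessions as Day 22, "Week 6 (Day 43 ± 3 days") and "Week 9 (Day 64 ± 3 days"). Protocol 4 reports the pivotal study's onset times from the first injection session as well: median 160 days for nodules and 55 days for papules.

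**The concern.** The 30-day cut falls inside the treatment course, before sessions 3 and 4. A reader who takes the later class to mean delayed lesions would be misled in subjects with several sessions, because a lesion arising days after a repeat injection is counted with lesions arising months later. The pivotal papule median shows how near this lies: an onset at 55 days in a subject with three sessions is 13 days after the third injection, yet falls in the later class. Time to onset by Fitzpatrick skin type is a secondary objective (SAP 3.2), and SAP 6.0 confines the onset analysis to the adverse events of interest, so these summaries carry that objective. The data for a second clock exist: Protocol 8.6 records session dates and locations, and Protocol 9.1.1 records event location and onset date. If the split blurred the distinction between early reactions and late lesions, and nothing else in the plan restored it, a long-term safety study would lose useful information.

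**Working it through.** **Inputs.** Target days 22, 43 and 64, each ± 3 days (SAP 5.3, Table 1); relative day = date minus first treatment date plus one (SAP 5.3); onset time = event start minus first treatment date (SAP 5.4); cut at 30 days (SAP 4.4.4.2).

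**1. Reproduce the schedule.** Target day = 7 × week + 1 gives 22, 43 and 64 for weeks 3, 6 and 9, as in Table 1. Onset time is relative day minus one, so sessions fall at 0, 21, 42 and 63 days. The Table 1 windows give 18–24, 39–45 and 60–66. If each visit is instead booked from the previous one (Protocol 12.1.2: "Subjects will be scheduled for next visit in three (3) weeks", ± 3 days), the ranges are 18–24, 36–48 and 54–72.

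**2. What the 30-day cut does.** After session 2, 30 − 21 = 9 days remain in the early class (6–12 with the window). After sessions 3 and 4 none remain: 30 − 42 = −12 and 30 − 63 = −33. The premise is correct.

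**3. Where a latest-session clock would differ.** Let L be the day of the last session in the affected area. A lesion changes class if its onset is later than day 30 on the first-injection clock and within 30 days of the most recent session. On target, consecutive sessions are 21 days apart, so no onset before the last session can be more than 21 days from the most recent one. The early class on the new clock is therefore every onset up to L + 30:

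| Sessions in the area | L (days) | Clocks disagree on onset days | New early class, in days from first injection |
|---|---|---|---|
| 1 | 0 | none | ≤ 30 |
| 2 | 21 | 31–51 | ≤ 51 |
| 3 | 42 | 31–72 | ≤ 72 |
| 4 | 63 | 31–93 | ≤ 93 |

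The visit windows do not alter this. The widest gap that Table 1 allows is 45 − 18 = 27 days, and 24 days if visits are booked one from the next. Both are below 30.

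**4. What the second clock would achieve.** The last column is the existing clock with a cut set by session count. With four sessions, an onset on day 90 is 90 − 63 = 27 days after the last session and would count as early, even if the lesion stemmed from the injection on day 0. One mixed class replaces another, and neither clock identifies the session responsible. Shown by skin type, the new split would also reflect any difference between groups in number of sessions.

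**5. Check against the pivotal onsets.** Papule median with three sessions: 55 − 42 = 13 days, so the class changes. Nodule median with four sessions: 160 − 63 = 97 days, late on both clocks.

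**6. What the plan already shows.** The Kaplan-Meier curve and the descriptive statistics keep onset in days, so onsets on days 31–93 can be read directly. The two-way split is the only one of these onset summaries that collapses them. The 120-day cut for the other events lies 120 − 63 = 57 days beyond the planned fourth session and raises no such question.

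**The case for a change.** The best argument for a second clock is that the later-than-30-days class is a mixture in multi-session subjects, that the tables by number of sessions give counts without timing, and that one labelled extra table would need no new data. All of that is true. What stands is a caution for the reader: this class means more than 30 days after first injection and must not be read as delayed relative to the last injection.

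It does not follow that the plan is deficient. The extra table would be optional and would carry its own ambiguity (step 4). It would have to be derived by area, since under Protocol 8.1 "the other side should continue to be treated until the target grade is achieved". It would also be thin where skin type matters most: with the planned minimum of 22 type IV subjects and the pivotal rate of 20/116 (17.2%, assumed to apply here), about 22 × 0.172 = 3.8 subjects would have a nodule or papule to split.

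Deferral is a fair further point. Protocol 11.1 says treatment "should be deferred until the inflammatory process has resolved and is controlled" and sets no time limit, so sessions may fall later than the schedule. The zone of disagreement then extends beyond day 93, and once a gap exceeds 30 days the simple cut in step 3 no longer describes the second clock. Even then, that clock would not show which injection caused the lesion.

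**Conclusion.** There is no error to correct. The first-injection origin is explicit, the same in SAP 4.4.4.2 and 5.4, and comparable with the pivotal study. It suits a single regimen in which every treated area is first injected at Visit 1, and the secondary objective prescribes no other origin. The split behaves exactly as defined, and the continuous summaries beside it keep the information that it collapses.

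The point touches only one descriptive split for nodules and papules, in subjects with more than one session, for onsets on days 31–51, 31–72 or 31–93 with two, three or four on-target sessions. With four sessions the upper end is 90–96 under the Table 1 windows, or 84–102 if visits are booked one from the next. The co-primary 5-year and the 2-year incidence endpoints do not depend on it. The share of lesions affected cannot be stated: the number of sessions per subject is not given, and the pivotal onset figures rest on about 8 + 2 = 10 subjects with nodules and 10 + 2 = 12 with papules.

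This assumes sessions within their windows, each treating the affected area, and complete event dates. It covers the public text only. SAP 4.4.4.1 and Protocol 13.5.4.1 are not visible and may contain more, but the conclusion does not depend on them.
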